7.3 SAMPLE SIZE/POWER

Acute toxicity. A total of 57 patients will be enrolled and will contribute to the hypothesis test of the acute toxicity rate. Since these are favorable risk patients, no loss to follow-up by 30 days post-XRT is expected. With 57 patients, there is 90% power for a chi-square test at a 1-sided 10% significance level, to test the null hypothesis that the acute toxicity rate is $\geq 35\%$ (clearly unacceptable) versus the alternative hypothesis that the acute toxicity rate is $\leq 20\%$. This analysis will be performed when 57 patients have 30 day post-XRT data.

Cosmesis at 2 years. The rate of excellent to good cosmesis on the Harvard scale will be scored at 2 years post-XRT. We anticipate that 3 patients will enroll on the study with fair cosmesis at baseline and they will be excluded from this endpoint. In addition, we anticipate that another 4 patients will be lost or have progressive disease before 2 years and who are not scored as fair or poor cosmesis (i.e., considered a failure) at a time point prior to 2 years and they will be excluded from this endpoint. Thus 50 patients will contribute to the analysis of whether excellent to good cosmesis is maintained at 2 years post-XRT. With 50 patients, there is 90% power for a chi-square test at a 1-sided 10% significance level, to test the null hypothesis that the cosmesis rate is $\leq 70\%$ (clearly unacceptable) versus the alternative hypothesis that the cosmesis rate is $\geq 85\%$.

7.4 TRIAL DURATION.

A total of 57 patients will be enrolled. With an expected monthly accrual of 2 patients, this study will enroll for approximately 2.5 years and the total duration of the study is approximately 4.5 years, in order to follow patients for 2 year cosmesis.

8 Safety and Adverse Events

The principal and secondary investigators will be responsible for detecting, documenting and reporting all events that meet the definition of an AE or SAE as defined in this protocol.

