A primary objective is to assess the rate of acute toxicity which will be tested by chi-square test at the end of the phase II study. But since accelerated partial breast radiotherapy with photons is a novel intensive treatment course, we have decided to continue Bayesian monitoring of acute toxicity throughout the course of the phase II study. Assuming a beta (1,5) prior, if the number of patients with Grade 3 or higher acute toxicity is greater than or equal to the number in the table below, then termination will be considered, because it is likely that the toxicity rate is $>20\%$, as noted by the Bayesian posterior probabilities.

Bayesian Rule for Acute Toxicity including skin changes				
Patients treated	20	30	40	50
Patients who experience acute toxicity	6	8	10	12
Posterior Prob [acute toxicity rate $>20\%$]	0.89	0.85	0.82	0.79
Action	Terminate enrollment			

CONFIDENTIAL

This material is the property of the University of Pennsylvania. Do not disclose or use except as authorized in writing by the study sponsor

7.2.4 Statistical Analyses.

The following are standard methods for data analysis which will be employed. Graphical analyses will include scatter plots, box plots, mean (\pm SE) plots and histograms. The distribution of continuous variables will be characterized with mean, median, standard deviation and range, while the distribution of categorical variables will be described with frequency, percentage and 95% CI. Toxicities will be categorized as acute or late and will be graded and tabled by toxicity type. The Grade 3+ acute toxicity rate and confidence interval will be calculated and a one sample chi-square test will be performed. The rate of excellent to good cosmesis at 2 years post-XRT and confidence interval will be calculated and a one sample chi-square test will be performed. Time to local failure and overall survival will be estimated by the Kaplan-Meier method.

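### The 90% power and one-sided 10% level in section 7.3 are large-sample figures that no fixed cut-off meets together at 57 or 50 patients; state the decision counts and their exact properties (minor)

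*Combined protocol and SAP*

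**What the plan says.** Section 7.3 sizes two primary tests.

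- **Acute toxicity:** "A total of 57 patients will be enrolled and will contribute to the hypothesis test of the acute toxicity rate", and "no loss to follow-up by 30 days post-XRT is expected". The null is a rate of at least 35% and the alternative a rate of at most 20%. The claim is "With 57 patients, there is 90% power for a chi-square test at a 1-sided 10% significance level".
- **Cosmesis at two years:** the null is a rate of at most 70% and the alternative at least 85%. The claim is "With 50 patients, there is 90% power for a chi-square test at a 1-sided 10% significance level".

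Section 7.2.4 gives the analysis for toxicity: "The Grade 3+ acute toxicity rate and confidence interval will be calculated and a one sample chi-square test will be performed". It words the cosmesis analysis the same way. Neither section states a decision count, says whether a continuity correction applies, or gives an exact error rate.

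Section 7.2.3 adds Bayesian monitoring of acute toxicity during phase II. Termination is to be considered at 6 or more events in 20 patients, 8 in 30, 10 in 40 or 12 in 50.

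**The concern.** With 57 or 50 patients the number of events takes only whole values, so the attainable error rates move in steps. A level and power taken from a smooth normal curve need not match any rule that can actually be applied. Two things follow.

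1. The stated pair of 10% level and 90% power may not be available from one cut-off. For toxicity, any excess error is the chance of accepting a rate that the plan itself calls clearly unacceptable.
2. Without a stated count or test version, a result on the boundary can be read either way, and the choice could be made after the data are seen.

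**Working it through.** **Inputs (section 7.3).** Toxicity: n = 57, p0 = 0.35, p1 = 0.20. Cosmesis: n = 50, p0 = 0.70, p1 = 0.85. One-sided level 0.10, z = 1.2816. No loss to 30 days.

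**1. Reproduce the stated power.** Large-sample formula for the uncorrected one-sample test:

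power = Φ{ [ |p0 − p1|·√n − z·√(p0(1 − p0)) ] / √(p1(1 − p1)) }

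- Toxicity: (0.15 × 7.550 − 1.2816 × 0.4770) / 0.4 = (1.1325 − 0.6113) / 0.4 = 1.303, so power is 90.4%. Solving for 90% gives n = 56.1, that is 57.
- Cosmesis: (0.15 × 7.071 − 1.2816 × 0.4583) / 0.3571 = (1.0607 − 0.5873) / 0.3571 = 1.326, so power is 90.8%.

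Both agree with the plan. With a continuity correction the toxicity power would be 87.2%, so the uncorrected version is evidently the one used for sizing.

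**2. Find the count at which the named test rejects (toxicity).** z = (x/57 − 0.35) / √(0.35 × 0.65 / 57), with standard error 0.0632.

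- x = 15: z = −1.375, p = 0.085, reject.
- x = 16: z = −1.097, p = 0.136, do not reject.

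The uncorrected rule is therefore 15 or fewer of 57.

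**3. Exact binomial properties for toxicity.** Level = P(X ≤ c | 0.35); power = P(X ≤ c | 0.20).

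| Accept if events ≤ | Exact level | Exact power |
|---|---|---|
| 14 | 6.2% | 84.8% |
| 15 | 10.7% | 90.9% |
| 16 | 16.9% | 95.0% |

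No row has level at most 10% and power at least 90%. The smallest sample at which one count does is 61 (16 or fewer: 9.5% and 91.2%).

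**4. The boundary result, 15/57.**

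| Version | One-sided p | Verdict at 10% |
|---|---|---|
| Uncorrected chi-square | 0.085 | toxicity acceptable |
| Continuity-corrected | 0.108 | not shown |
| Exact binomial | 0.107 | not shown |

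In a fixed sample, the probability of exactly 15 events at a true rate of 20% is 90.9% − 84.8% = 6.1%.

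**5. Cosmesis.** At 40/50, z = (0.80 − 0.70) / √(0.70 × 0.30 / 50) = 1.543, p = 0.061. At 39/50, z = 1.234, p = 0.109. The rule is 40 or more of 50.

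- 40 or more: exact level 7.9%, power 88.0%.
- 39 or more: exact level 13.9%, power 93.7%.

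At 40/50 the continuity-corrected p is 0.082 and the exact p is 0.079, so all three versions agree. Here the issue is only a two-point overstatement of power.

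**6. Effect of the section 7.2.3 limits if enforced.** The binomial path is followed patient by patient, stopping at 6/20, 8/30, 10/40 or 12/50, and success requires reaching 57 with 15 or fewer events.

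- True rate 35%: probability of success 2.3%.
- True rate 20%: probability of success 59.8%.

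With the feasibility-stage limits in section 7.1.4 enforced as well, these become 1.5% and 44%.

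**The case against.** The strongest reply is that the plan names one method throughout, that its power reproduces by that method, and that it never claims exact binomial properties. The named test has exact power of 90.9%, slightly above what is stated, and its level is over by only 0.7 points at a 10% phase II threshold. Because only the uncorrected version reproduces 90%, the version can be inferred. All of this stands. It is why the point is minor, and why a reader who inferred an arithmetic error would be wrong.

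Three other stronger readings also fail.

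- **That the trial's power is 84.8%.** That figure belongs to the cut-off of 14, which the uncorrected test does not use. Nor is it true that no rule of any kind meets the targets. Rejecting at 14 or fewer and, with probability (10 − 6.23) / (10.66 − 6.23) = 0.85, at 15 would have exactly 10% error and about 90.0% power. The plan provides for no such randomisation, so the statement is limited to non-randomised cut-offs.
- **That a confidence interval would contradict the test because the test is approximate.** Section 7.2.4 specifies 95% intervals for categorical variables; no 80% interval appears in the plan. An exact 95% interval has an upper limit above 35% even at 14/57 (37.8%). That disagreement comes from setting a two-sided 95% interval beside a one-sided 10% test, not from the choice between chi-square and exact methods.
- **That 10.7% is the error the trial will have.** It is a fixed-sample figure. If the phase II limits are enforced, the error is far lower. The boundary result then also becomes rare: reaching 15/57 needs at most 11 events in the first 50 patients and at least 4 in the last 7, with probability about 0.25% at a true rate of 20%. Since termination is only to be considered, the fixed-sample figures remain a fair reference, but they need that condition beside them.

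What survives is that the stated pairs are not jointly delivered and that the plan does not settle a 15/57 result in advance.

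**Conclusion.** The point holds as a minor one. For toxicity the plan offers either a level of 10.7% with 90.9% power or a level of 6.2% with 84.8% power, not 10% with 90%. For cosmesis it offers 7.9% with 88.0%. One count, 15/57, changes verdict with the version of the test.

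These figures assume 57 and 50 evaluable patients, independent outcomes, true rates at the stated null and alternative values, and no early stopping. The last assumption matters most: enforcing the phase II limits moves the toxicity power from 90.9% to about 60%, a much larger change than anything due to discreteness.

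**What to change.** In sections 7.2.4 and 7.3:

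- Name the test version: uncorrected chi-square, continuity-corrected or exact binomial.
- State the decision counts with their exact properties. For toxicity, choose either 14 or fewer of 57 (level 6.2%, power 84.8%) or 15 or fewer of 57 (level 10.7%, power 90.9%). For cosmesis, use 40 or more of 50 (level 7.9%, power 88.0%).
- Say that these are fixed-sample figures, and that if the limits of 6/20, 8/30, 10/40 and 12/50 are enforced, the toxicity test at 15 or fewer of 57 has about 60% power and 2.3% type I error.

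The cost is a few lines of text and a slightly less favourable stated level or power. No additional patients or procedures are needed.

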8.1 Definitions

Adverse Event

An *adverse event* (AE) is any unfavorable and unintended sign, symptom, illness/disease (new or exacerbated) or experience that develops or worsens in severity temporally associated with the use of the proton APBI and is considered by the investigator to be definitely or probably related to the treatment. Intercurrent illnesses or injuries should be

CONFIDENTIAL

This material is the property of the University of Pennsylvania. Do not disclose or use except as authorized in writing by the study sponsor

regarded as adverse events. Abnormal results of diagnostic procedures are considered to be adverse events if the abnormality:

- results in study withdrawal
- is associated with a Serious Adverse Event (SAE)
- is associated with clinical signs or symptoms
- leads to additional treatment or to further diagnostic tests
- is considered by the investigator to be of clinical significance

AEs Not to Include:

- Medical or surgical procedures (e.g. endoscopy, appendectomy); the condition that leads to the procedure is an AE.
- Situations where an untoward medical occurrence did not occur (elective and/or convenience admission to a hospital).
- Anticipated day-to-day fluctuation of pre-existing disease(s) or condition(s) present or detected at the start of the study that do not worsen in grade or severity.
- The disease/disorder being studied, or expected progression, signs, or symptoms of the disease/disorder being studied, unless more severe than expected for the subject's condition.
- Grade 1 adverse events that are not in the following categories: fatigue, skin, breast, ribs, heart, and lungs.

Serious Adverse Event

Adverse events are classified as serious or non-serious. A **Serious Adverse Event** is any medical occurrence that at any dose:

- fatal
- life-threatening

Note: (the subject was at risk of death at the time of the event, not events that hypothetically might have caused death if it were more severe)

- hospitalization or prolongs hospital stay (hospitalization signifies in general, the subject has been detained [at least an overnight stay] at the hospital or emergency department for observation/treatment that would not have been appropriate in a physician's office or outpatient setting).

Note: Hospitalization for elective treatment, diagnostic purposes or a pre-existing condition that did not worsen from baseline is not considered an AE or SAE.

Hospitalization/prolonged hospitalization to allow for study efficacy assessment is not an SAE.

- results in persistent or significant disability or incapacity

Note: A substantial disruption of a person's ability to conduct normal life functions. Not intended to include experiences of relatively minor medical significance such as uncomplicated headache, nausea, vomiting, diarrhea, influenza, accidental trauma (e.g. sprained ankle) which may interfere or prevent everyday life functions but do not constitute a substantial disruption.

- a congenital anomaly or birth defect
- an important medical event

CONFIDENTIAL

This material is the property of the University of Pennsylvania. Do not disclose or use except as authorized in writing by the study sponsor

Important medical events are those that may not be immediately life threatening, but are clearly of major clinical significance. They may jeopardize the subject, and may require intervention to prevent one of the other serious outcomes noted above. For example, drug overdose or abuse, a seizure that did not result in in-patient hospitalization or intensive treatment of bronchospasm in an emergency department would typically be considered serious.

All adverse events that do not meet any of the criteria for serious should be regarded as ***adverse events (AEs) per protocol definition.***

Clinical Laboratory and Other Safety Assessments

Any abnormal laboratory test result (.e.g. hematology, clinical chemistry, urinalysis) or other safety assessment (e.g. ECGs, radiological scans, vital signs), including those that worsen from baseline and are felt to be **clinically significant** in the medical and scientific judgement of the investigator are to be recorded as AE or SAEs if they meet the definition of an AE, as defined above. However, any clinically significant safety assessments that are associated with the underlying disease, unless judged by the investigator to be more severe than expected for the subject's condition, are **not** to be recorded as AEs or reported as SAEs.

The investigator will exercise his/her medical and scientific judgment in deciding whether an abnormal laboratory finding or other abnormal assessment is clinically significant. This assessment will be documented on the lab report or in a timely clinic/progress note.

Disease Related Events and/or Disease-Related Outcomes Not Qualifying as SAEs

An event that is part of the natural course of the disease (e.g. disease progression) does not need to be reported as an SAE. Progression of the subject's cancer will be clearly recorded in the clinic/progress note. Death due to progressive disease is not an SAE. However, if the progression of the underlying disease is greater than that which would normally be expected for the subject or if the investigator considers that there was a causal relationship between the investigational agent/treatment/device and the disease progression, then this must be reported as an SAE. Any new cancer must be reported as an SAE.

Preexisting Condition

A preexisting condition is one that is present at the start of the study, prior to administration or exposure to any protocol agents/treatments/devices. A preexisting condition should be recorded as Medical History and becomes an adverse event if the frequency, intensity, or the character of the condition worsens during the study period as defined by the protocol.

Radiation Effect

Radiation side effects are typically divided into those that occur acutely (during radiation and up to 1 month after radiation) and those that occur later (>1 month post-radiation).

CONFIDENTIAL

This material is the property of the University of Pennsylvania. Do not disclose or use except as authorized in writing by the study sponsor

Common acute radiation side effects include fatigue and radiation dermatitis. The potential late effects of APBI using proton therapy include fibrosis of breast tissue adversely affecting cosmesis and/or causing breast pain, rib fractures, pulmonary fibrosis, and radiation-induced heart disease. Another rare but serious late side effect is the development of second tumors. It is hoped that proton radiation will substantially reduce both acute and late side effects by reducing the amount of normal tissue that is irradiated.

For acute and late radiation effects CTCAE 5.0 will be employed.

Assessment of Causality

The investigator must assess the relationship between the investigation aspect of the protocol and the occurrence of each AE/SAE. The investigator will use clinical judgment to determine the relationship. Alternative causes, such as natural history of the underlying diseases, concomitant therapy, other risk factors, and the temporal relationship of the event to the investigational aspect of the protocol should be considered and investigated.

Post-study Adverse Event

All unresolved adverse events should be followed by the investigator until the events are resolved, the subject is lost to follow-up, or the adverse event is otherwise explained. At the last scheduled visit, the investigator should instruct each subject to report any subsequent event(s) that the subject, or the subject's personal physician, believes might reasonably be related to participation in this study.

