7.1.3 Endpoints

Primary Endpoints

Feasibility will be based on multiple radiation planning and treatment parameters. Should a patient experience one of the following events, treatment will be deemed infeasible:

- a) Patient cannot be given treatment because anatomy is such that a dosimetrically satisfactory treatment plan cannot be devised. For example, the dosimetry is unsatisfactory if < 95% of the target volume is covered by 95% of the dose.
- b) Patient is unable to tolerate more than 20% of treatments using proton radiotherapy (i.e., >2 of the 10 fractions). This can be for any reason, including the inability to set the patient up within acceptable limits of tolerance, or the patient is unable to tolerate treatment position or immobilization for duration of treatment. Thus, up to 20% (i.e., 2 of the 10 fractions) of treatments could be delivered using photons.
- c) Patient is unable to complete all treatment within 5 days of the estimated date of treatment completion or requires a treatment break of \geq than 5 days.
- d) No more than 20% of patients experience an acute toxicity, as defined below.

Acute toxicity is defined as any grade 3 or higher hematologic or non-hematologic toxicity, including skin changes, as graded by the NCI CTC Version 5.0, observed **within 30 days from the end of radiotherapy**, which is probably or definitely related to proton therapy.

Secondary Endpoints

Late toxicity is defined as any grade 3 or higher hematologic or non-hematologic toxicity which occurs more than 30 days after end of therapy. Late toxicities will be graded according to the CTC Version 5.0. Special attention will be paid to fibrosis and cosmesis. The time frame for late toxicity is open-ended because late toxicities have been known to occur a year or more after therapy. Follow-up for late toxicity will cease when a patient experiences disease progression since 2nd line therapies may then be initiated.

Cosmesis will be scored using the Harvard scoring system (scale = excellent, good, fair, poor) and CTC Version 5.0. In addition, cosmesis will be scored by the cosmesis and breast pain subscales of the Breast Cancer Treatment Outcomes Scale (BCTOS) instrument.

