Patients who experience acute toxicity	2	2	3	4
Posterior Prob [acute toxicity rate $> 20\%$]	0.80	0.62	0.70	0.76
Action	Terminate enrollment			

7.1.5 Statistical Analyses.

Feasibility: The posterior probability that this feasibility rate is 90% will be calculated. The feasibility rate and exact 90% CI will also be computed. The reasons why patients were not feasible will be tabulated.

Acute toxicity: All toxicities observed within 30 days from end of therapy will be graded by CTC Version 5.0 and tabulated. The posterior probability that this acute toxicity rate is 20% will be calculated.

Late toxicity: All toxicities observed later than 30 days from end of therapy will be graded by the CTC Version 5.0 and tabulated.

Cosmesis will be scored using the Harvard scoring system and CTC Version 5.0. BCTOS will be scored every 6 months and fold changes over time will be described and plotted.

Clinical efficacy: Local control (time to local failure) and overall survival will be estimated by the Kaplan-Meier method. It is likely that these time-to-event outcomes will be summarized after completion of the phase II study.

Estimation of Event Rates: The table below displays the 90% exact binomial confidence intervals based on 12 patients treated.

No. of Events	%	90% exact CI	No. of Events	%	90% exact CI
0	0.0	17.5*	7	58.3	31.5 , 81.9
1	8.3	.43 , 33.9	8	66.7	39.1 , 87.7
2	16.7	3.0 , 43.8	9	75.0	47.2 , 92.8
3	25.0	7.2 , 52.7	10	83.3	56.1 , 97.0
4	33.3	12.3 , 60.9	11	91.7	66.1 , 99.6
5	41.7	18.1 , 68.5	12	100.0	82.5*
6	50.0	24.5 , 75.5			* 90% 1-sided CI

7.2 PHASE II STUDY.

7.2.1 Design and Objectives.

Once feasibility and safety are established, then the phase II portion of the study will commence. A total of 57 patients will be enrolled; 12 patients are included from the feasibility study and 45 additional patients are enrolled in the phase II study. The two primary objectives are: to determine whether the rate of Grade 3+ acute toxicity is $\leq 20\%$ and whether the rate of maintained excellent to good cosmesis is $\geq 85\%$ at 2 years post-XRT. Only patients with excellent or good cosmesis at baseline contribute to this analysis.

7.2.2 Endpoints.

Acute Toxicity, as defined in Section 7.1.3

Cosmesis, as scored by the Harvard scale, CTC Version 5.0 and BCTOS scoring systems.

Late Toxicity, Local control and overall survival, as defined in Section 7.1.3

7.2.3 Rules for Early Termination for Acute Toxicity.

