8.2 Assessing and Recording Adverse Events

At each contact with the subject, the investigator must seek information on adverse events by specific questioning, examination and review of clinical documentation (e.g. lab reports, radiology reports). Information on all adverse events, as defined by the protocol, should be recorded immediately in the source document and also on the adverse event Case Report Form (CRF). It is preferred that events are recorded by diagnosis (where applicable) instead of through signs/symptoms/test results. For example, shortness of breath, chest pain and nausea may have been confirmed as a myocardial infarct through lab test and an ECG, therefore, "MI" or "myocardial infarct" or "heart attack" should be recorded instead of all of the signs/symptoms.

All adverse events meeting the protocol definition, occurring during the study period must be recorded. Full documentation of an event includes start/stop dates, event, grade, expectedness, attribution and outcome. The clinical course of each event should be followed until resolution, stabilization, or until it has been determined that the study treatment or participation is not the cause.

All Adverse and Serious Adverse Events will be assessed using NCI Common Terminology Criteria for Adverse Events version 5 (CTCAE 5.0). Expectedness will be captured for all adverse events

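### The AE definition in section 8.1 requires probable or definite relatedness, so other Grade 3+ events need not be recorded, contrary to sections 7.1.3, 7.1.5, 8.1 and 8.2

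*Combined protocol and SAP*

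**What the plan says.** In section 8.1 the AE definition ends with a condition on cause: the event must be one that "is considered by the investigator to be definitely or probably related to the treatment". The lead-in to section 8 makes investigators responsible for the events that meet the protocol's AE or SAE definition. Section 8.2 repeats the limit: "All adverse events meeting the protocol definition, occurring during the study period must be recorded".

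Other text assumes a wider set of events:

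- **8.1, next sentence.** It begins "Intercurrent illnesses or injuries should be" and continues after a page break by classing such illnesses and injuries as AEs, whatever their cause.
- **8.1, Assessment of Causality.** "The investigator must assess the relationship between the investigation aspect of the protocol and the occurrence of each AE/SAE", with other possible causes to be considered.
- **8.2.** "Full documentation of an event includes start/stop dates, event, grade, expectedness, attribution and outcome".
- **7.1.5.** "All toxicities observed within 30 days from end of therapy will be graded by CTC Version 5.0 and tabulated".
- **7.1.3, late toxicity.** "Late toxicity is defined as any grade 3 or higher hematologic or non-hematologic toxicity which occurs more than 30 days after end of therapy". No relatedness condition follows.

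The primary acute toxicity endpoint in 7.1.3 has a filter of its own. It takes Grade 3+ toxicity within 30 days of the end of radiotherapy "which is probably or definitely related to proton therapy". Section 7.2.2 carries that endpoint into phase II.

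**The concern.** Attribution ought to be a judgement made about a recorded event. Here it is made first and decides whether a record is required at all. An event called only possibly related, or unrelated, is not an AE under 8.1, so nothing in 8.2 obliges anyone to enter it on the AE form.

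This matters more than usual for two reasons. The trial is open and single-arm, so no concurrent group shows how often such events occur without protons. Attribution will also be uncertain in practice. Section 5.1 allows chemotherapy from two weeks after radiotherapy, inside the 30-day acute window, and section 5.2 allows endocrine therapy during radiotherapy. The acute endpoint includes hematologic toxicity, for which systemic therapy is an obvious alternative explanation.

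At stake are the completeness of the all-toxicity tables and the ability to review, after the fact, which Grade 3+ events were kept out of the primary endpoint and why.

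**Working it through.** **1. Does the definition control recording?** Take a Grade 3 event on day 20 after radiotherapy, judged possibly related. It fails the relatedness clause in 8.1, so it is not an AE. The section 8 lead-in and 8.2 require documentation only of events that meet the definition. No AE-form entry is therefore required.

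**2. Can the other passages hold at the same time?**

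- *Intercurrent illness (8.1).* An illness that merely coincides with treatment would not normally be probably or definitely caused by it. It is an AE under this sentence and not one under the sentence before.
- *Causality assessment (8.1) and attribution field (8.2).* If only probable and definite events enter, the assessment can do no more than separate those two grades. Section 8.2 also follows events until treatment is found not to be the cause, an outcome the definition has already ruled out.
- *All toxicities tabulated (7.1.5).* The table promises every toxicity to day 30. The AE form is required to hold only the related ones. Section 7.2.4 likewise plans tables of toxicity by grade and type for phase II.
- *Late toxicity (7.1.3).* This is defined without regard to cause, so an AE dataset filtered on cause cannot supply it in full. Section 8.3.1 also ends AE collection 30 days after the last treatment, so late events must rest largely on the toxicity assessments in 6.4.

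**3. Does the clause alter the primary analysis?** First, the plan's own figure. Section 7.3 gives n = 57, null rate p0 = 0.35, alternative p1 = 0.20, one-sided 10% level and 90% power. With the normal approximation:

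- Null standard error: √(0.35 × 0.65 / 57) = 0.0632
- Alternative standard error: √(0.20 × 0.80 / 57) = 0.0530
- Power: Φ[(0.15 − 1.2816 × 0.0632) / 0.0530] = Φ(1.30) = 0.904
- Critical count: 57 × (0.35 − 1.2816 × 0.0632) = 15.3, so the null is rejected at 15 or fewer events

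The stated 90% is reproduced, and the AE wording enters none of these terms.

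Now the count itself. Under 7.1.3 a counted event is Grade 3+, within 30 days, and probably or definitely related. Section 8.1 requires the same relatedness. Applying that filter twice gives the same set as applying it once, so deleting it from 8.1 adds no event to the primary count. The Bayesian monitoring in 7.1.4 and 7.2.3 uses the same endpoint and is unchanged too.

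**4. What does change?** The all-cause Grade 3+ count is the related events plus the rest. The AE form must hold the first group and need not hold the second. The effect is therefore on the all-toxicity tables, on any all-cause rate, and on review of attribution.

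**5. Are there other routes?** The physician toxicity assessments (6.3, 6.4) and the DSMC notice of Grade 3+ events (8.3.3) state no relatedness filter and may capture some of the second group.

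**The case against.** The strongest reply is that this is a wording problem with no effect on the trial's conclusions. The primary endpoint already excludes events not judged probably or definitely related, so a change to 8.1 moves no count, stopping boundary or power figure. That stands.

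A reader might infer more: that the AE definition itself hides misattributed Grade 3+ events from the primary toxicity test and so makes a false declaration of acceptable toxicity more likely. The documents do not support this. Any such effect comes from the filter in 7.1.3 and would be the same before and after 8.1 is corrected. Sizing it would also need a misattribution rate that the documents do not give, and would have to allow for the stopping rules in 7.1.4 and 7.2.3.

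Nor do the documents support saying that excluded events leave no trace. Source records exist, and the routes in 6.3, 6.4 and 8.3.3 carry no stated filter. They are only a partial answer: after the section 8 lead-in, the events in 8.3.3 can be read as AEs in the restricted sense, and nothing says that toxicity assessments must generate an AE-form entry. It is also unsettled whether SAEs inherit the restriction. Section 8.1 classifies AEs as serious or non-serious, but it words the SAE definition around any medical occurrence and makes any new cancer reportable as an SAE.

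Finally, attribution errors run in both directions, so the bias is not necessarily downward. There is an asymmetry in review, however. An event wrongly called related is on the form and can be challenged, while one wrongly called unrelated may not be there.

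**Conclusion.** The contradiction is real and should be corrected. Section 8.1 makes relatedness a condition of being an AE, 8.2 ties recording to that definition, and at least five other provisions need events recorded without that condition. The consequence is limited to record-keeping and supporting analyses: the all-toxicity tables may be incomplete, and exclusions from the primary endpoint may be hard to audit.

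The effect on the primary count, stopping rule and power is nil. The number of Grade 3+ events that would go unrecorded cannot be estimated from the documents. The conclusion assumes that site staff follow 8.1 and 8.2 literally. If they already enter every toxicity, the data loss would be small, but the text would still contradict itself.

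**What to change.** - Delete the relatedness clause from the AE definition in 8.1.
- In 8.2, require AEs to be recorded with grade and attribution whatever the cause, covering at least every Grade 3+ event to day 30.
- Keep the probable-or-definite condition only in the 7.1.3 acute toxicity endpoint, so that the primary test and monitoring stay as they are.
- In 7.2.4, add one supporting analysis: the all-cause Grade 3+ acute rate with its confidence interval, beside the related rate and using the same denominator and method.

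The cost is a wording amendment and a few extra AE-form entries over a 30-day window in 57 patients. It is best done promptly, since events not recorded at the time may be hard to recover later.
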